Patient Health Questionnaire – 9 ⁴⁵	Validated measure of depressive symptoms	EHR	x	x
General Anxiety Disorder - 7 ⁴⁶	Validated measure of anxiety symptoms	EHR	x	x
Tobacco use	Important CV risk factor in Life's Essential 8.	Eureka	x	x
Sleep hours	Important CV risk factor in Life's Essential 8.	Eureka	x	x
Blood pressure	Important CV risk factor in Life's Essential 8.	EHR	x	x
Weight/Body Mass Index (BMI)	Important CV risk factor in Life's Essential 8.	EHR	x	x
Cholesterol	Important CV risk factor in Life's Essential 8.	EHR	x	x
Hemoglobin A1c	Important CV risk factor in Life's Essential 8.	EHR	x	x
Self-reported minutes/week of moderate to vigorous physical activity	Important CV risk factor in Life's Essential 8.	Eureka	x	x
Steps/day	Objective measure of physical activity in people with available data.	Eureka	x	x
Six-minute walk distance ⁴⁷	Objective exercise capacity measure collected routinely as an outcome in CR programs.	EHR	x	x
Satisfaction with the intervention(s) ⁴⁸	Measure of acceptability.	Eureka		x
Net promoter score	Measure of acceptability	Eureka		x
Time and costs	Custom questionnaire to help estimate costs.	Eureka		x
Consumption of food	Custom questionnaire to report consumption of distributed food	Eureka		x
Cardiovascular Events	Events include CV hospitalizations for myocardial infarction, heart failure, stroke, and deaths.	EHR		x
Number of CR sessions attended	Attending a greater number of CR sessions is associated with greater benefit. ⁴⁹	EHR		x
Number of FIM meal units	Primary outcome of study. We will be able to determine this outcome in all participants. Because some participants will receive groceries and some participants will receive meals, we will define this outcome as a meal "unit" received from POH. A meal unit is defined as 7 packaged meals (delivery), 1 grocery box (delivery), 1 set (5 or 7) of packaged meals (pick-up), or 1 grocery distribution (pick-up). We will collect number of FIM meal units throughout participants' 3-month study participation and throughout their insurance authorization period.	POH		x

	We will also collect number of FIM meal units for their dependents, if applicable.			
--	--	--	--	--

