We will conduct optional individual semi-structured interviews in a convenience sample of study participants and staff with regard to implementation of the interventions. Participants will be asked to provide verbal consent for the interviews. Interviews will be audio-recorded and transcribed without reference to the participant identify.

Phase 2 Participant Compensation

Participants will receive \$50 for completing eVisit 1 (Month 0) and \$50 for completing eVisit 2 (Month 3) and \$50 for completing the optional interview.

Comparators

Intervention A: Navigation: Navigation will occur at both the health system and FIM program levels. The health system navigator will be separate personnel from CR program staff to limit effects on usual care. Navigation will include: motivational interviewing,²⁴ patient-determined visits (i.e., phone, video, or in-person visits depending on patient preference), and delivery of a structured approach to participation: 1) explain the program, 2) explain the benefits, 3) provide positive endorsement, 4) describe process to enroll, 5) welcome questions, 6) address barriers to attendance, and 7) provide with follow-up information.²³ Health system navigation will include at least 3 attempts to contact participant for each individual session. Participants will have 1 weekly navigation session until the participant enrolls in the FIM program or declines further contact. Scripts will be refined based on Phase 1 activities. FIM program navigation will include individual in-person, video, or telephone contacts by FIM staff to participants to address participation barriers. FIM navigation contacts will occur on a weekly basis until the participant has achieved sufficient engagement (receipt of 8 FIM meals) or the participant declines further contact. Scripts will be refined based on Phase 1 activities.

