For each intervention, the null hypothesis is the mean number of FIM meals received will not differ between experimental and control groups. Intervention-specific analyses will use separate generalized estimating equation (GEE) log-Poisson models with robust standard errors to estimate the mean (95%CI) count per group and experimental: control risk ratio (RR);⁵² models will be adjusted for the opposite experimental arm and baseline 6MWD as a measure of health status. An exploratory GEE model adding the A*B interaction term to models will be conducted and displayed in a forest plot of RR (95%CI) of each intervention arm (n=21) versus UC alone (n=21). Log-Poisson models will be used to estimate mean satisfaction and the proportions who initiated and engaged. We will use standard ANCOVA models to analyze 3-month changes in continuous outcomes (e.g., self-efficacy) and rank-based ANCOVA for changes in discrete outcomes (e.g., Life's Essential 8).⁵³ All ANCOVA models include the baseline value of the outcome as a covariate, the opposite experimental arm, and 6MWD.

We will also describe inputs, activities, outputs, outcomes using descriptive quantitative measures (e.g., counts, proportion, mean, standard deviation) and narrative description. We will qualitatively describe participant and staff responses from interviews and study artifacts using a rapid analysis template³⁵ based on the Theory of Planned Behavior,³⁶ Consolidated Framework for Implementation Research,⁵⁴ and emergent themes.

Cost Estimation

As part of this project, we will estimate costs of usual care and the interventions.

Usual care (costs may apply to all participants):

- Staff (health system): we will estimate the time it takes for staff to complete the following activities:
 - Draft MyChart message
 - Send MyChart message to participant
 - Complete and send referral for to POH
- Staff (POH): we will estimate the time it takes for staff to complete the following activities:
 - Receive and review referral from health system
 - Schedule participant intake
 - Conduct participant intake
 - Engage with participant during the course of the usual care program
- Participant: we will ask participants to estimate time and costs using a custom questionnaire, administered at the 3-month eVisit. Time and costs will be related to scheduling POH visits and receiving POH meals or groceries.

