- POH Supplies, Capital Equipment, Facilities, and Other costs: we will consider POH Supplies, Capital Equipment, Facilities, and Other costs on a per participant and/or per meal basis.

Intervention A – Navigation (costs will only apply to participants randomized to these groups):

- Staff (health system): we will ask staff to record or estimate the time it takes to:
 - Schedule session with participant
 - Prepare for session with participant
 - Engage in session with participant

- Complete follow-up tasks from session with participant
- Hand off to POH
- Staff (POH): we will estimate the time it takes for staff to:
 - Receive hand off from health system
 - Schedule session with participant
 - Prepare for session with participant
 - Engage in session with participant
 - Complete follow-up tasks from session with participant
- Participant: we will estimate participant time from the reported staff time for scheduling and engaging with participant.
- Supplies, Capital Equipment, Facilities, and Other costs: we will estimate overhead costs based on staff time per participant.

Intervention B – Text Messaging (costs will only apply to participants randomized to these groups):

- Staff (health system):
 - Time to draft text messages
 - Time to program messages into Eureka
- Cost of delivering messages through Twilio, the service used by Eureka
- Participants will report monthly cost of phone service, include text messaging on the Time and Costs questionnaire.

Data Collection, Retention, and Monitoring

Data for Phase 1 will be recorded in study records on UCSF REDCap or UCSF OneDrive.

The primary data collection source for Phase 2 will be the Eureka Research Platform. This platform includes participant-facing interfaces for data collection, along with investigator- and clinical research staff-facing interfaces for data entry and management.

Participant data for Phase 2 will also be collected from the UCSF Electronic Health Record and entered in the Eureka Research Platform.

Data Collection Instruments

The Investigator will prepare and maintain adequate and accurate source documents designed to record all observations and other pertinent data for each participant.

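### Participant time for navigation is taken only from staff time, which cannot contain travel to in-person sessions, so participant cost is biased low for anyone who makes a separate trip

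*Combined protocol and SAP*

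**What the plan says.** Under Cost Estimation, Intervention A – Navigation, participant time has one stated source: "we will estimate participant time from the reported staff time for scheduling and engaging with participant". For health-system staff, the same list says "we will ask staff to record or estimate the time it takes to" schedule, prepare for, hold and follow up a session, and hand the participant off to POH. POH staff time is to be estimated over a similar list. The last line for this intervention scales overhead on staff time. No line names participant travel or out-of-pocket cost.

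Under Comparators, Intervention A, health-system navigation consists of "patient-determined visits (i.e., phone, video, or in-person visits depending on patient preference". Navigation by the food program may also be face to face: "FIM program navigation will include individual in-person, video, or telephone contacts by FIM staff to participants to address participation barriers". On contact effort, the section adds: "Health system navigation will include at least 3 attempts to contact participant for each individual session".

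The participant's own report is the Time and Costs questionnaire. Table 2 describes it only as "Custom questionnaire to help estimate costs", at month 3. Under Cost Estimation, Usual care, its content is given as follows: "Time and costs will be related to scheduling POH visits and receiving POH meals or groceries". The text-messaging list adds the monthly cost of phone service to the same questionnaire.

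**The concern.** Staff time is a fair proxy for participant time while both are on the same call. It fails for an in-person session that the participant travels to. The journey and the fare fall on the participant alone, and neither scheduling minutes nor session minutes can hold them. This does not depend on how carefully staff keep their records.

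What is at stake is the participant component of the navigation cost estimate. Self-report is planned for participants' time and costs in reaching POH services and for phone cost under text messaging. Participant time in navigation is the one item that rests wholly on a staff proxy. Navigation contacts are weekly until a stopping condition is met, so an omission per session can recur. The background section lists transportation among the access problems participants face, and Table 2 notes that the EQ-5D-5L can support cost-effectiveness analysis. A later user of the cost data could therefore be misled about participant burden. Staff cost and the trial's endpoints are not touched.

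**Working it through.** The protocol states no time or cost figure for navigation, so there is no planned number to reproduce. The check is a comparison of the sections, followed by an illustration on assumed inputs.

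**Comparison**

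| Element of participant burden | Described source | Captured? |
|---|---|---|
| Time in the session | Staff engaging time | Yes |
| Time on a scheduling contact | Staff scheduling time | Yes |
| Travel time to an in-person session | None described | No |
| Fares or other out-of-pocket cost of that trip | None described | No |
| Scheduling POH visits, receiving food | Questionnaire (Usual care) | Yes |
| Phone service | Questionnaire (Text Messaging) | Yes |

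In-person sessions are an allowed mode at both the health-system and the food-program level, so rows 3 and 4 can occur under the plan as written.

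**Illustration of travel alone (all inputs assumed)**

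- Session 30 minutes and answered scheduling call 5 minutes, so the staff-based figure is 30 + 5 = 35 minutes.
- In-person share f = 0, 0.25 or 0.5; extra round-trip travel t = 0, 30 or 60 minutes.
- Average actual participant time = 35 + f × t.
- Relative error = 35 / (35 + f × t) − 1.

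| f | t | Actual minutes | Error |
|---|---|---|---|
| 0 | any | 35 | 0% |
| 0.25 | 30 | 42.5 | −18% |
| 0.25 | 60 | 50 | −30% |
| 0.5 | 30 | 50 | −30% |
| 0.5 | 60 | 65 | −46% |

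For one in-person session with its own trip, the figures are 35 / (35 + 30) − 1 = −46% and 35 / (35 + 60) − 1 = −63%. Fares come on top and are not in these figures. Where there is no extra trip (f = 0 or t = 0), the error is nil.

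**Unanswered attempts, if they were carried over (assumed)**

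Suppose that two unanswered attempts of 5 minutes each were logged as scheduling and assigned to the participant, with no travel. The estimate would be 35 + 10 = 45 against 35 actual minutes, or +29%. With two attempts of 3 minutes it would be 41 against 35, or +17%. The protocol does not say that this will happen.

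Varying both elements together (0 to 2 unanswered attempts of 1, 3 or 5 minutes, with the values of f and t above) gives 81 combinations: 31 too high, 35 too low and 15 exact, from −46% to +29%. The documents therefore fix neither the sign nor the size of a net error. Only the direction of the travel omission follows from the text.

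**The case against.** The travel gap is conditional. In-person contact is one of three modes and is chosen by the patient. The location is not stated, staff might go to the participant, and a session might coincide with a rehabilitation visit or a weekly food pick-up. In those cases extra travel could be nil. The questionnaire's items are not reproduced, so one can say that no navigation travel item is described, but not that none exists. Its described scope is also wider than POH food, since it takes in phone-service cost. Estimating participant time from staff time is a disclosed, low-burden simplification in a pilot. All of this stands. It limits the size of the problem but does not supply a source for travel when a trip is made.

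A reader might go further and infer that unanswered contact attempts will be counted as participant time, so that navigation cost is wrong in both directions. The documents do not support that. The plan estimates participant time from staff time spent scheduling and engaging with the participant, which can be read as time in contact. It gives no one-for-one conversion and does not say where failed calls are recorded. The rule of at least three attempts sets a minimum contact effort and is stated for health-system navigation only. What remains is a risk: no category or instruction separates failed attempts from scheduling. Staff minutes spent on failed attempts are in any case a genuine staff cost.

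Nor do the documents commit to a formal comparison of navigation cost with text-messaging cost. They promise to estimate the costs of usual care and of the interventions.

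**Conclusion.** The point holds for travel. Followed exactly, the stated rule gives too low a participant cost for anyone who makes a separate trip to an in-person navigation session. The size cannot be derived, because the in-person share, the location of sessions and the travel involved are not given; the illustrated 0 to −46% per average session rests wholly on assumed inputs. The conclusion assumes that at least some participants make trips only for navigation and that the questionnaire contains no more than is described.

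Possible over-counting from unanswered attempts is an unspecified detail worth closing, not a demonstrated error. The effect is confined to the participant component of navigation cost. Cost is not among the primary or secondary endpoints, so no trial hypothesis is affected. This is a cheap improvement, of modest importance.

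**What to change.** 1. In Cost Estimation, Intervention A, have health-system and POH staff record the mode of each completed session (phone, video, in person).
2. Add to the month-3 Time and Costs questionnaire, for the two arms with navigation, an item on travel time and out-of-pocket cost for trips made only for navigation. Limiting it to such trips avoids counting again the journeys for food pick-up or cardiac rehabilitation.
3. As a secondary safeguard, state that participant time is based on minutes of completed contact, so that time on unanswered attempts counts as staff cost only.

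The cost is one field on the staff record, one or two questions on an existing survey, and a sentence in the protocol. The downside is slightly more burden for staff and participants, and travel recalled at month 3 will be approximate. If the questionnaire already has such an item, it is enough to say so in the Cost Estimation section.
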